#### **7.12.6.3 Proportion of subjects receiving repeat injection.**

The proportion of subjects receiving repeat injections will be compared between the two treatment groups using a Chi-Square test. The proportion of subjects receiving a repeat injection will be summarized by treatment group.

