Each subject will have the option of receiving 1 supplemental OL TF injection of SP-102 ("repeat injection"). To qualify for the repeat injection, subjects must meet Repeat Injection Inclusion Criteria, NPRS pain score in the affected leg, and investigator judgment, which includes a safety evaluation demonstrating no signs or symptoms of adrenal suppression or other safety concerns. The repeat injection may be administered between Weeks (W) 4 and 20. Eligible subjects will receive OL SP-102 repeat injection regardless of their initial treatment assignment (SP-102 or placebo).

In case of inadequate control of radicular pain, up to [REDACTED] will be allowed per day. The subject should be instructed to avoid use of acetaminophen within 6 hours prior to recording an NPRS score. Doses of rescue medication and time taken will be collected in the eDiaries until W12 and thereafter as a concomitant medication.

The subject will complete the eDiary twice daily approximately 12 hours apart (± 2 hours) to record their NPRS scores for pain in the previous 12 hours for 12 weeks following index injection. Thereafter, NPRS scores will be recorded at clinic visits.

All subjects will be seen at the clinic on D15, and every 4 weeks (ie, W4 [D29], W8 [D57], W12 [D85], W16 [D113], W20 [D141], and W24 [D169]) after the DB index injection for up to 24 weeks. Subjects receiving the OL repeat SP-102 injection will also be seen at the clinic 14 days after the repeat injection and continue the DB planned visits as well. The subject will also be contacted by telephone by the site staff 2 days after each IP injection to discuss their progress, any medications they are taking, and if they have had any adverse events (AEs).

The study visits and the planned efficacy analysis after all enrolled subjects have completed W12 are depicted in [Figure 3.1](#).

Figure 3.1: Study Schematic

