3.3.3 Stopping Rules

A single occurrence of an adverse event of special interest (AESI) precludes the subject receiving a repeat injection. Three occurrences of the AESI of the same type across the study will trigger stopping of all further dosing until implementation of a safety review.

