### 5 SAMPLE SIZE

## 6 RANDOMIZATION

Using an Interactive Web Response System (IWRS), on D1, the site staff or research pharmacist will contact the IWRS after the Investigator has confirmed that the subject fulfills all the inclusion/exclusion criteria. The IWRS will assign a randomization number to the subject, which will be used to link the subject to a treatment arm. The research pharmacist will prepare the appropriate IP and deliver it to study staff in preparation for injection.

A randomization schedule will be employed to facilitate effective randomization and allocation concealment. The schedule will involve a block randomization technique, randomly assigning participants within blocks based on a 1:1 allocation ratio. The randomization schedule will be stratified by study site.

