## 7.12 Efficacy Analyses

All statistical tests will be performed using a two-tailed 5% overall significance level, unless otherwise stated. All comparisons between treatments will be reported with 95% confidence intervals (CI) for the difference. Pain profiles through the first four weeks will be presented by the treatment received for the first injection (SP-102, Placebo). Moreover, pain profiles through 12 weeks will be presented by treatment received for second injection (SP-102/SP-102, PBO/SP-102, SP-102/none, PBO/none). Also, the ‘site’ indicated in this section refers to the final pooled sites as described in [Section 7.2.10](#).

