### 7.12.6.1 PGIC at Week 2, Week 4, Week 8, and Week 12.

The PGIC is a seven-point scale (1 to 7, where 1 is very much improved and 7 is very much worse) that allows patients to rate their global impression of change. PGIC will be collected after randomization at Weeks 2, 4, 8, 12, 16, 20, and 24. For analysis, a subject will be classified as either PGIC responder, that is, a PGIC response of 1: very much improved or 2: much improved or a PGIC non-responder, that is, all other PGIC responses (recorded as 3-7 in the scale). Subjects who do not complete the measure at the timepoint of interest will also be considered non-responders. The number and percentage of subjects reporting each of the seven PGIC response levels will also be summarized by visit and treatment. The analysis will utilize separate Chi-Square tests for Week 2 and Week 4 where the p-value of the treatment difference will be presented. Separate logistic regression models with treatment, site, and Pain Catastrophizing Scale group as factors will also be used to compare the treatment groups at each week (Week 2 and Week 4) using the two treatment groups. The odds ratio of SP-102 vs placebo at Weeks 2 and 4, and its corresponding 95% CI and p-value will be presented.

Separate Chi-Square tests and similar logistic regression analyses will be applied at Weeks 2, 4, 8, and 12 using the treatment group with four arms: SP-102/SP-102, PBO/SP-102, SP-102/none, PBO/none. The following odds ratios at Weeks 2, 4, 8, and 12 and the corresponding 95% CIs and p-values will be presented:

- SP-102/none vs. PBO/none

- SP-102/SP-102 vs. PBO/none
- SP-102/none vs. PBO/SP-102
- SP-102/SP-102 vs. PBO/SP-102

A summary of the assessments at Weeks 16, 20, and 24 will be presented.

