#### **7.12.6.2 The time (days) to repeat injection of SP-102**

The time to repeat injection of SP-102 will be analyzed using survival analysis methods. Subjects that do not receive a repeat injection will be censored at 20 weeks, and subjects who discontinue the study prior to 20 weeks without receiving a repeat injection will be censored at the time of discontinuation. The Kaplan-Meier estimator will be used to estimate the quartiles of the time to repeat injection in days. A Cox proportional hazards model will be utilized to test the treatment difference in time to repeat injection while adjusting for site, and Pain Catastrophizing Scale. The response variable of the Cox model will be time to repeat injection. The treatment group categories for this analysis will be the SP-102 and placebo groups. The quartiles and their corresponding 95% CIs from the Kaplan-Meier estimation, and the hazard ratio of SP-102 to placebo with its 95% CI and p-value will be presented. A survival plot of time to repeat injection will also be presented. Listings of time to repeat injection will be presented.

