#### **7.12.6.15 Proportion of subjects requiring rescue medication**

The proportion of subjects requiring rescue medications will be compared across treatment arms using a Chi-Square test. This endpoint will be analyzed separately for the first 4 weeks (two groups), and the first 12 weeks (four groups).

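### The crude chi-square tests on repeat injection and 4-week rescue have no legible rule for early leavers, and safety refusals count as no repeat needed

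*SAP*

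**What the plan says.** SAP 7.12.6.3: "The proportion of subjects receiving repeat injections will be compared between the two treatment groups using a Chi-Square test". SAP 7.12.6.15: "The proportion of subjects requiring rescue medications will be compared across treatment arms using a Chi-Square test", with a 4-week comparison of the two randomized groups and a 12-week comparison of four groups. Neither section states a denominator or says what happens to subjects who leave without the event. SAP 7.12.6 applies the mITT and PP populations, and neither definition, as far as it is legible, requires completion.

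The neighbouring endpoints do have rules:

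- Time to repeat (7.12.6.2) and time to first rescue (7.12.6.14) censor leavers at discontinuation.
- For PGIC (7.12.6.1), "Subjects who do not complete the measure at the timepoint of interest will also be considered non-responders". CGIC (7.12.6.12) and the pain responders (7.12.6.10) are handled in the same way.
- Cumulative rescue use is imputed after withdrawal (7.12.6.13), and rescue-free days are rescaled to time on study (7.12.6.16).

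Protocol 3.1 allows a repeat only between Weeks 4 and 20. The investigator's judgment must include "a safety evaluation demonstrating no signs or symptoms of adrenal suppression or other safety concerns". Protocol 3.3.3 adds: "A single occurrence of an adverse event of special interest (AESI) precludes the subject receiving a repeat injection". In the time-to-repeat analysis, "Subjects that do not receive a repeat injection will be censored at 20 weeks" unless they discontinue earlier.

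**The concern.** Both proportions are listed among the secondary efficacy endpoints (Protocol 5.2.8.3), and the sequential procedure in SAP 7.12.6.19 extends to the other secondary endpoints. The natural reading is that fewer repeats and less rescue are better.

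A subject who leaves before Week 4 cannot receive a repeat, and one who leaves in the first days has had little time to use rescue. With no leaver rule, both stay in the denominator as event-free, which is the favourable outcome. The arm that loses more subjects then looks better for that reason alone.

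A second problem affects only the repeat endpoint. A subject who would otherwise have had a repeat but is refused for safety is indistinguishable in 7.12.6.3 from one who did not need it. In 7.12.6.2 that subject, if still in the study, is carried event-free to 20 weeks. Some grounds for refusal could be caused by SP-102, so a harm could lower its repeat rate.

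**Working it through.** **Inputs from the documents.** About 400 subjects randomized and a target of 332 completing Week 4 (Protocol synopsis); 1:1 allocation (SAP 6), so n = 200 per arm; two-sided 5% tests (SAP 7.12). The two totals imply a loss of 1 − 332/400 = 17%. This is back-solved, because no dropout rate is legible. The plan gives no figure for repeat or rescue proportions, so there is none to reproduce.

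**Assumptions.** Repeat risks, rescue risks, loss by arm and refusal rates are not in the documents and are assumed throughout.

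**Formulas.** If all leavers go before Week 4, observed proportion = true risk × (1 − loss). With d the absolute difference between arms A and B and p̄ their mean proportion:

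- s0 = √(2p̄(1 − p̄)/n)
- s1 = √([pA(1 − pA) + pB(1 − pB)]/n)
- rejection probability ≈ Φ((d − 1.96·s0)/s1), plus a negligible opposite tail

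**A true difference, 60% placebo v 45% SP-102.**

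- Full follow-up: (0.150 − 1.96×0.0499)/0.0494 = 1.06, power 85%.
- Loss of 17% in each arm: 0.60×0.83 = 49.8% and 0.45×0.83 = 37.4%. The difference falls from 15 to about 12.5 points: (0.1245 − 1.96×0.0496)/0.0492 = 0.55, power 71%.
- Loss of 22% placebo and 12% SP-102 (mean 17%): 0.60×0.78 = 46.8% and 0.45×0.88 = 39.6%, a difference of 7.2 points, power 31%. Here the bias works against SP-102.

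**No true difference, 60% in both arms.**

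- Equal loss leaves equal proportions and the nominal 5% error.
- Loss of 22% in one arm and 12% in the other gives 46.8% v 52.8%: (0.060 − 1.96×0.0500)/0.0499 = −0.76, false rejection about 22%, favouring the arm that lost more.
- At 50% risk the same split gives 39.0% v 44.0% and 17%. Across risks of 30% to 70% it gives 11% to 29%.

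**Dropout spread over follow-up.** The cases above place all loss before Week 4, which is the worst case. The table shows simulations with loss spread evenly, no true difference, 200 per arm and 1,500 trials per row. An unadjusted log-rank test that censors leavers stands in for the planned Cox test. Entries are trials falsely favouring SP-102 (nominal 2.5%).

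| Endpoint and risk | Loss SP-102 / placebo | Chi-square | Log-rank |
|---|---|---|---|
| Repeat, 50% | 22% / 12% | 7.1% | 2.9% |
| Repeat, 50% | 27% / 7% | 20.1% | 2.1% |
| Rescue to 4 weeks, 70% | 22% / 12% | 7.0% | 2.0% |
| Rescue to 4 weeks, 70% | 27% / 7% | 19.3% | 2.1% |

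With the repeat split reversed (12% / 22%), the chi-square test falsely favours placebo in 7.1% of trials.

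**Safety refusals, repeat endpoint only.** Assume equal 17% loss before Week 4, 50% risk, and refusals in the SP-102 arm alone. The placebo proportion is 0.50×0.83 = 41.5%.

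- 5% refused: 41.5%×0.95 = 39.4%, with 6.2% of tests falsely favouring SP-102.
- 10% refused: 41.5%×0.90 = 37.35%, with 13.3%.

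Censoring does not repair this. In simulation the chi-square and log-rank tests gave 5.9% and 6.3% at 5% refused, and 13.9% and 14.7% at 10% refused.

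**The case against.** A reader might infer that dropout as well as harm will read as SP-102 benefit. The documents do not support that for dropout. The direction follows whichever arm loses more, and nothing in the documents points to heavier loss on SP-102. Heavier placebo loss would count against SP-102.

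A reader might also infer that the SAP prescribes counting leavers as no event. It is silent: that is the literal consequence of a crude proportion in a population that does not require completion. Protocol 5.2.4 and 5.2.8.4 are redacted, as is part of the mITT section, and they could hold a rule. No redaction is visible in SAP 7.12.6.3 or 7.12.6.15.

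Further points on the other side:

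- Leavers are already censored in 7.12.6.2 and 7.12.6.14, and early terminations with reasons are tabulated by group (SAP 7.5). An imbalance would be visible, but these separately reported tests would remain uncorrected.
- Refusals may be rare. Protocol 4.2.2 lists three AESI types, and three events of one type pause dosing, so at most 2×3 = 6 can occur without a pause (3% of 200 if all fall in one arm). Refusal for other safety concerns has no such ceiling.
- The endpoint is receipt of a repeat. Counting an untreated subject as repeated in the main analysis would redefine it. This objection stands, so any such analysis must be supportive.
- A Kaplan-Meier comparison overlaps with the planned time-to-event analyses and assumes independent censoring, which may fail if subjects leave because of pain. This also stands, and is why a second, unfavourable-leaver run is needed.

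**Conclusion.** The concern holds in limited form. As legibly written, the test in 7.12.6.3 and the 4-week test in 7.12.6.15 count event-free leavers as no event. That biases them toward the arm with more loss and dilutes a true difference when loss is equal. With all loss before Week 4, and the assumed risks and 17% overall loss, the cost is a power drop from 85% to 71%, or about 22% false rejection under a 10-point imbalance. With loss spread over follow-up, the simulated 22%/12% splits give about 7% in the favoured direction, against a nominal 2.5%.

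The safety-refusal problem is real in direction, applies to the repeat endpoint only, and is shared by the time-to-repeat analysis. Its size cannot be determined from the documents, and AESI refusals alone are likely few. These are non-key secondary endpoints and the primary conclusion is unaffected, but the change should be made before unblinding because a better estimate is available from data the SAP already derives.

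**What to change.** 1. Unless a redacted rule already covers leavers (in which case cite it in both sections), replace the crude chi-square in 7.12.6.3 and in the 4-week part of 7.12.6.15. Use the between-arm difference in Kaplan-Meier cumulative incidence, at 20 weeks for repeat and Day 29 for rescue, with a 95% CI. Censor leavers at discontinuation and state the independent-censoring assumption.
2. Add one supportive run that counts event-free leavers as events, matching the treatment of PGIC, CGIC and pain responders.
3. Keep the repeat endpoint as receipt of a repeat. Report safety refusals by arm, and add a supportive version of 7.12.6.2 and 7.12.6.3 that treats a refusal as an unfavourable or competing event. If it is treated as competing, show the incidence of refusal beside that of repeat, because the latter alone would still look lower.

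Cost: SAP wording, a little more programming, some overlap with the planned time-to-event analyses, and somewhat higher headline proportions. A field for the reason and date of refusal is needed if not already captured. No change to treatment or to the repeat-injection criteria is involved.

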#### **7.12.6.4 The mean change from Baseline (D1) to Week 2, Week 4, Week 8, and Week 12 in the mean NPRS average pain score in the affected leg.**

Baseline and post-baseline values for this endpoint is obtained as discussed in [Section 7.12.1](#). A similar approach in modeling the restricted maximum likelihood (REML)-based MMRM as in the primary analysis will be applied for this endpoint. Mean change from baseline to Week 2 and Week 4 will be analyzed and presented by the treatment received for the first injection (SP-102, Placebo). Mean change from baseline for the first 12 weeks (Weeks 2, 4, 8, and 12) will utilize similar MMRM model except that the outcome variable will be change from baseline in mean weekly NPRS average pain score in the affected leg at Weeks 2, 4, 8, and 12, and the fixed effects are as follows: treatment (four groups: SP-102/SP-102, PBO/SP-102, SP-102/none, PBO/none ), week (2, 4, 8, 12), site, Pain Catastrophizing Scale group (<30 or ≥30), baseline averaged daily leg

pain score, and the treatment-by-week interaction. Mean change from baseline for Weeks 2, 4, 8, and 12 will be summarized by treatment received for second injection (SP-102/SP-102, PBO/SP-102, SP-102/none, PBO/none).

As part of this analysis, comparisons will test the mean LS mean differences between the following groups:

- SP-102/none vs. PBO/none
- SP-102/SP-102 vs. PBO/none
- SP-102/none vs. PBO/SP-102
- SP-102/SP-102 vs. PBO/SP-102

NPRS average scores are also collected at visits (Weeks 16, 20, and 24) after visit 12. This data will not be included in the model but will be included in the summary table.

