3.5.8 Other Assessments

Pain Catastrophizing Scale: PCS ([Appendix K](#)) is used to assess pain as a baseline characteristic only at Screening ([Sullivan-1995](#)). It was developed to quantify a subject's pain experience by asking how they feel and what they think about when they are in pain. Items on this scale were developed from clinical and experimental research on catastrophic thinking and its relation to experience of pain. The PCS is a 13-item instrument that can be completed and scored in less than 5 mins. The PCS requires a reading level of approximately Grade 6.

Hospital Anxiety and Depression Scale: HADS ([Appendix L](#)) is commonly used to determine a subject's anxiety and depression levels. The scale is comprised of 14 items rated on a scale of 0-3; 7 items focused on anxiety symptoms and 7 items focused on depression symptoms. The HADS will be used for inclusion criteria and completed at Screening only. A score of 11-14 on either the depression or anxiety subscale is indicative of moderate symptomatology. A score of ≥ 15 on either the depression or anxiety subscale is indicative of severe symptomatology ([Snaith-1994](#), [Turk-2015](#)). Subjects with HADS scores ≥ 15 will be excluded from this study ([Zigmond-1983](#)).

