#### **7.12.5 Key Secondary Analysis**

Baseline ODI is defined as the last ODI assessment score prior to the first injection on D1. The change in ODI total score from baseline will be analyzed using the mITT and PP Analysis Populations. This endpoint will be analyzed using the analysis of covariance (ANCOVA) model where change from baseline in ODI score at Week 4 will be the response variable with fixed effects for treatment (two groups: SP-102 or placebo), site, Pain Catastrophizing Scale group (<30 or

≥30), and baseline ODI. The treatment group categories for this analysis will be the SP-102 and placebo groups. A summary of the observed and change from baseline ODI total score will be presented by visit and treatment group jointly for both the primary and secondary analysis periods. Listings of all 10 topic scores and total scores will be presented.

The following SAS code will be used for this key secondary analysis;

[REDACTED]

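### The SAP cuts the Pain Catastrophizing Scale at 30 in the key secondary and most other adjusted secondary models, giving up a little precision that the recorded score could supply

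*SAP*

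**What the plan says.** The key secondary analysis (SAP 7.12.5, change in ODI at Week 4) is an ANCOVA with "fixed effects for treatment (two groups: SP-102 or placebo), site, Pain Catastrophizing Scale group", cut at 30, plus baseline ODI. The four-group NPRS model to Week 12 (SAP 7.12.6.4) has the same term: "Pain Catastrophizing Scale group (<30 or ≥30". The cut is repeated for ODI to Week 12 (7.12.6.7), PainDETECT (7.12.6.8), BPI-SF (7.12.6.9), NPRS responders (7.12.6.10), CGIC (7.12.6.12) and cumulative rescue use (7.12.6.13).

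Two places differ in wording. The PGIC analysis (7.12.6.1) uses "Separate logistic regression models with treatment, site, and Pain Catastrophizing Scale group as factors" and does not restate the cut. The Cox model for time to repeat injection (7.12.6.2) tests treatment "while adjusting for site, and Pain Catastrophizing Scale", with neither a group nor a cut. Time to first rescue dose (7.12.6.14) is to be analysed in the same way, so its coding is open too.

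Protocol 3.5.8 describes the instrument: "The PCS is a 13-item instrument that can be completed and scored in less than 5 mins". It says that the scale "is used to assess pain as a baseline characteristic only at Screening". Randomisation is stratified by site alone (Protocol 3.4.3; SAP 6). The covariate list of the primary model (SAP 7.12.2) is redacted. The chi-square tests for repeat injection and rescue use (7.12.6.3, 7.12.6.15) and the one-way ANOVA of rescue-free days (7.12.6.16) do not use PCS.

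**The concern.** A cut at 30 presupposes a numeric total, so the score is available for every subject who can be placed in a group. Nothing in the randomisation calls for a two-level factor, and the readable text gives no reason for choosing 30. The same models keep other baseline measures as scores: baseline ODI in 7.12.5, baseline leg pain in 7.12.6.4 and the PainDETECT total in 7.12.6.8. A linear PCS term uses one degree of freedom, as the two-level factor does.

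If PCS predicts outcome in a graded way, the factor treats everyone below 30 as alike and everyone from 30 up as alike. Outcome variation within each group that the score could have explained stays in the residual. In the linear models this widens the standard error of the treatment effect slightly. That matters most for ODI at Week 4, because the testing sequence in SAP 7.12.6.19 stops at the first non-significant result and ODI stands directly after the primary endpoint.

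Separately, the time-to-event models leave the coding of a prespecified covariate undecided.

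**Working it through.** **Inputs from the documents.** About 400 randomised and 332 to complete Week 4 (Protocol synopsis); 1:1 allocation, hence 166 per arm; two-sided 5% level (SAP 7.12).

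**Inputs that the documents do not give.** Power, effect size, SD and dropout rate are redacted, so 332 cannot be re-derived. The two sample sizes agree with each other if 17% are lost by Week 4 (1 − 332/400 = 0.17, an inference). The plan states no figure for the effect of cutting PCS. The share p of subjects at or above 30, the shape of the score and the PCS–outcome correlation ρ are all assumptions below.

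**Step 1: share of the covariate's explained variance that the cut keeps.** For a normal score and a linear relation, kept = φ(z)² / [p(1 − p)], where φ is the standard normal density and z is the normal quantile at 1 − p.

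- p = 0.50: z = 0, φ = 0.3989, kept = 0.1592/0.25 = 0.637, so 36% is lost.
- p = 0.35: kept = 0.603, so 40% is lost.
- p = 0.20: z = 0.842, φ = 0.2800, kept = 0.0784/0.16 = 0.490, so 51% is lost.

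The loss depends heavily on the assumptions. With a normal score it is 66% at p = 0.10 and 78% at p = 0.05. Six bounded shapes on an assumed 0–52 range, with p between 11% and 48%, gave losses of 26% to 46%. If the true relation is a step at 30, the loss is zero.

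**Step 2: effect on the treatment comparison in a linear model.** Let ρ be the correlation of PCS with outcome given the other covariates. The variance ratio, cut against score, is (1 − ρ² × kept)/(1 − ρ²). This treats PCS as nearly unrelated to site and baseline score, so that the kept share carries over. For example, with ρ = 0.3 and kept = 0.490, the ratio is (1 − 0.0441)/0.91 = 1.050.

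**Step 3: equivalent subjects and power.** Subjects = 332 × (ratio − 1). Power is for 166 per arm, where the model with the score would have 80%.

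| ρ | p = 0.50: ratio; subjects; power | p = 0.20: ratio; subjects; power |
|---|---|---|
| 0.1 | 1.0037; 1.2; 79.9% | 1.0052; 1.7; 79.8% |
| 0.2 | 1.0151; 5.0; 79.4% | 1.0213; 7.1; 79.2% |
| 0.3 | 1.0359; 11.9; 78.6% | 1.0505; 16.8; 78.0% |

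The standard error is the square root of the ratio: 0.2% wider at the low end (ρ = 0.1, p = 0.50) and 2.5% wider at the high end (ρ = 0.3, p = 0.20). Stronger correlations would raise the cost, to 23–32 subjects at ρ = 0.4 and 40–57 at ρ = 0.5. These are correlations that must remain after site and, where the model has it, the baseline score.

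The formula in Step 2 is for linear models. It is not applied to the logistic or Cox models.

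**The case against.** The strongest reply is that this is a preference. The cut is prespecified and made on a variable measured before randomisation, so the two-arm comparison remains valid. A linear term also assumes a functional form, and if risk rises sharply near 30 the factor is the better choice. The cost is small, and a reason for 30 may lie in redacted text. All of this stands. It limits the point to a cheap gain in precision, but it does not show that the cut is needed.

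Four stronger readings are tempting, and the documents do not support them.

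- A reader might infer that the cut is known to discard a third to a half of the covariate's information. That is a normal-score result for particular shares. The documents give no share, distribution or relation, and other assumptions gave 26% to 78%, or nothing for a step. It is also a share of what PCS explains, not of the trial's information.
- A reader might extend the point to all efficacy models. The primary model's terms are redacted, and several tests omit PCS. The references elsewhere to the primary MMRM suggest a common PCS term but do not show one.
- A reader might expect smaller standard errors in the PGIC, CGIC and responder models. These are logistic. Fuller adjustment there tends to raise the standard error of the log odds ratio while moving the conditional estimate away from the null, and the odds ratio being estimated changes. Any gain is in power.
- A reader might say that the Cox model contradicts the rest by using the score. Its text does not say that the score is continuous. It may be shorthand for the group, so the fault is missing detail.

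**Conclusion.** The point holds as a minor matter of efficiency. PCS is cut at 30 in the key secondary ANCOVA and in most other adjusted secondary models, with no design reason visible. Using the score would normally sharpen the linear analyses slightly. Under the stated assumptions (normal score, linear relation, 20% to 50% at or above 30, ρ of 0.1 to 0.3), the gain is about 0.4% to 5% in variance, or up to 2 power points. Validity is not at issue in the two-arm comparisons. The four-group comparisons are formed after randomisation, and the statement about bias is not extended to them. The unstated coding in the Cox model needs no assumption to be worth correcting.

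**What to change.** Before unblinding:

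- In the ANCOVA, ANOVA and MMRM models that now use the PCS group, enter the PCS total score as a continuous covariate, linear or as a simple spline. Otherwise, give the reason for the cut at 30.
- Use the same coding in the logistic models for consistency, without expecting smaller standard errors there.
- State the PCS coding in SAP 7.12.6.2, which also settles 7.12.6.14.
- Keep the <30/≥30 split for descriptive tables or subgroups.

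The cost is SAP wording and one term in the model code. A linear term uses no extra degree of freedom, a spline uses a few, and no new data are needed. The downside is an assumed functional form.
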